1 BACKGROUND/SCIENTIFIC RATIONALE

Previous studies evaluating the effect of needle priming with heparin for liver biopsies have shown that heparinized needles improved histologic yield and tissue adequacy.^{1,2} With regards to pancreatic lesions, two retrospective studies showed that needle priming with heparin during EUS fine needle aspiration (FNA) of pancreatic solid lesions was not superior to conventional methods on tissue yield, sample adequacy, bloodiness, and number of passes.^{3,4} In contrast, a recent crossover RCT from Taiwan, found that among 50 patients with solid pancreatic masses, EUS-guided biopsy with a heparinized needle obtained longer white tissues with less blood contamination than with conventional EUS-FNB.⁵ However, the study measured tissue length with macroscopic on-site evaluation (MOSE), which is prone to investigator and measurement bias. In addition, the investigators used the same needle for each patient at the time of the crossover to the 2nd intervention, which introduces the possibility of needle contamination in those who were randomized to undergo sampling with the heparinized needle first. Finally, EUS sampling was performed using an old needle design not commercially available in the United States (20-gauge EchoTip ProCore needle) and by a single endoscopist, which limits the external validity of the results. Although these results are important, they cannot be generalizable and need to be confirmed in high-quality RCTs.

When sampling pancreatic masses with EUS-FNN, multiple passes are often performed to improve diagnostic accuracy and reduce false negative results. However, the impact of successive EUS-FNB passes on tissue quality is unknown. This may have a direct impact on specimens collected for purposes other than diagnostic histopathology, since the endoscopist typically reserves the first FNB passes for clinical histopathology and may collect the last passes for personalized medicine applications (e.g. next generation DNA or RNA sequencing).⁶ However, it is unclear whether successive passes will have the same tissue quality, as needles may progressively become contaminated with blood.

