2 OBJECTIVES

Primary objective:

- *Determine whether heparin priming of FNB needle improves tissue quality as compared to standard FNB for EUS-tissue acquisition of pancreatic masses.*

Secondary objectives:

- *Determine whether heparin priming of FNB needle improves cellularity.*
- *Determine whether heparin priming of FNB needle reduces blood contamination.*
- *Determine whether heparin priming of FNB needle improves histologic yield.*
- *Determine whether increasing number of FNB passes affects tissue quality, block contamination, and histologic yield.*
- *Determine the incremental diagnostic yield with a second or third FNB pass as compared to a single FNB pass.*

Hypothesis:

We hypothesize that the tissue quality of EUS-FNB specimens of pancreatic masses decreases with increasing pass number due to blood contamination. This blood contamination can be ameliorated with priming of the needle with an anticoagulant such as heparin, resulting in improved tissue quality of EUS-FNB of pancreatic masses.

Anticipated Results

- *We anticipate that histologic yield will decrease and blood contamination will increase with increasing number of FNB passes*
- *We anticipate that the intervention of heparin priming of the biopsy needle will decrease blood contamination and increase histologic yield.*

Trial design

- Single center, double-blind, superiority, parallel-group, 1:1 ratio, randomized controlled trial

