3 EXPECTED RISKS/BENEFITS

There are no immediate benefits to participating in this study. Of note, IF a diagnosis of malignancy is made on the tissue obtained for research by a blinded clinical pathologist AND the diagnosis was not made on the passes obtained for clinical purposes, the patient will be notified. In this event, either the PI or one of the co-investigators (all of which are practicing physicians) will reach out to the patient personally to inform them of the discrepancy and make arrangements for the research block to be submitted to pathology for further evaluation. Furthermore, the patient's physician will be notified, and the patient will be referred to the appropriate medical specialist to treat the incidentally found condition.

The known or expected risks are:

- 1) Bleeding - EUS fine needle aspiration and EUS FNB rarely (<0.01%) cause bleeding but this is not expected to be increased measurably by the one additional pass made for research purposes. The risk of bleeding will be minimized by the use of experienced gastroenterologists who will perform the EUS FNBs with Doppler assistance to identify and avoid intervening vasculature during needle puncture.
- 2) Pancreatitis - A risk of EUS-FNB is pancreatitis, which is inflammation of the pancreas that is uncommonly severe. The reported risk ranges from 0-2% in the literature. It is unknown whether increased numbers of FNB passes increases the risk of pancreatitis. The risk of pancreatitis as a complication will be minimized by the use of experienced gastroenterologists who will perform the EUS procedures.
- 3) Infection - EUS fine needle aspiration and EUS FNB rarely (<0.01%) cause infection cases but this is not expected to be increased by the one additional pass made for research purposes.
- 4) Prolongation of procedure time - Acquisition of additional specimens during EUS will extend procedure duration by no more than 5 to 10 minutes. The only risk associated with this would be additional discomfort. This risk will be minimized through the continued use of sedative and pain medications given during the procedure. As per the standard of care, vital signs including oxygen saturation, heart rate, blood pressure, and cardiac rhythm will be continuously monitored.

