- Intervention group: The FNB needle will be flushed with 1 mL of heparin (100 USP/mL) and then flushed with air. Pass 1, 2, and 3 will be collected in separate jars and sent to pathology, as per standard clinical procedures. The study will pay for the cost of utilizing and submitting extra jars to pathology so that no extra cost is incurred to the patient for participating in the study. Between passes, after tissue is extracted from the needle, the needle will be flushed with 1 mL of heparin (100 USP/mL) and flushed with air before next pass is made.
- Control group: FNB will be performed as current standard methods in the medical procedure unit without the use of heparin priming. Pass 1, 2, and 3 will be collected in separate jars and sent to pathology, as per standard clinical procedures. The study will pay for the cost of utilizing and submitting extra jars to pathology so that no extra cost is incurred to the patient for participating in the study. Between passes, after tissue is extracted from the needle, the needle will be flushed saline and or air as per current standards of care.

If proceduralist feels that it is unsafe to continue with the research protocol during the procedure (examples would include inadequate tissue acquisition in the clinical jar, or clinical instability of patient during procedure), he or she reserves the right to withdraw the patient from the protocol. For patient safety, the proceduralist will not be blinded to whether the patient was randomized to the heparin or non-heparin arm. If the proceduralist deems more than 3 passes are needed for clinical purposes, the extra passes will go into a fourth jar.

Tissue Analysis:

H&E slides from the passes 1, 2, and 3 (which will be requested from pathology) will be compared in the following manner:

- A blinded clinical pathologist will examine each slide and determine
 - Is a tissue diagnosis able to be made?
 - Is the tissue adequate quality? The pathologist will create a reference scoring system and rate specimens accordingly.
- In parallel, using the HALO® image analysis platform (Indica Labs), each slide will be digitally scanned. The number of cells present on each H&E slide (cell-based analysis), the amount of blood present on each H&E slide (area-based analysis), and the size of each biopsy will be quantified (area-based analysis).

Tracking and labelling system

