7 DATA COLLECTION AND MANAGEMENT PROCEDURES

Collection of medical record data for this study will include the following:

Initial collection:

- Patient demographic data:
 - Age
 - Sex
 - BMI
 - Pack Years
 - Presence of Diabetes, Type 1 or 2
 - Alcohol use
 - History of Pancreatitis
 - History of IPMN (intraductal papillary mucinous neoplasms)
 - Prior Cancer History

Follow up collection (approximately 4 weeks post-procedure):

- Was patient reached for follow-up?
- Did patient develop post-procedural complications?
- Did patient need interventions for post-procedural complications?
- Was hospital admission required for post-procedure complication?
- Did patient require repeated EUS for sampling?
- Age Patient demographic data:

Chart review at end of study (after 98 patients collected)

- Development of new pancreatic disease other than cancer
- Overall survival (date of death)
- Cancer Stage
 - If resectable, did patient receive surgery?
 - If yes
 - What surgery (distal pancreatectomy vs Whipple?)

- Final surgical staging
- Tumor grade
- Chemotherapy treatment
 - Palliative, neoadjuvant, or adjuvant chemo
 - Regimen (FOLFIRINOX, Gemcitabine/abraxane, Gemcitabine/cisplatin)
- ECOG score
- Final Diagnosis

. Data will be pulled from patient's medical charts via both DataDirect and chart review. Regarding data management we will seek assistance with the MICHR database development service. The study team may collect data from each research participant for up to 5 years from when they were consented. This data will be stripped of patient name and stored using REDCap; only the study team members have access to this database. On the database, patient identity will not be discernable to the casual observer. As indicated in section 6, separate from this, a spreadsheet key matching the specimen ID to the patient name and medical record number will be kept in a password and network protected database. Only study team members will have access to this spreadsheet.

SCHEDULE OF EVENTS8 DATA ANALYSIS

Primary Outcomes

- Heparin priming increases cellularity captured in fine needle biopsies
- Heparin priming decrease blood contamination in fine needle biopsies

Secondary Outcomes

- Successive fine needle biopsy passes result in more blood contamination
- Successive fine needle biopsy passes have lower cellular yield
- Successive fine needle biopsy passes have more blood contamination
- Need for repeated procedure (at U of M)

Exploratory Outcomes

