- Identify correlations in patient metadata (i.e. tumor grade, cancer stage) and tissue quality, cellular yield, and blood contamination

Tissue analysis:

H&E slides from the pass 1, 2, and 3 (which will be requested from pathology) will be compared in the following manner:

- A blinded clinical pathologist will examine each slide and determine
 - Is a tissue diagnosis able to be made?
 - Is the tissue adequate quality (pathologist will make a reference scoring system and rank specimens accordingly)

In parallel, using image processing software, the number of cells present on each H&E slide will be quantified, the amount of blood present on each H&E slide will be quantified by area quantification, and the tissue yield on each H&E slide will be quantified by area quantification.

Statistical Comparisons using image analysis:

The student *t* test will be utilized to assess if there is a significant difference in the following:

- Blood contamination area between passes 1, 2, and 3 in the heparin group
- Blood contamination area between passes 1, 2, and 3 in the non-heparin group
- Blood contamination area in pass 1 between the heparin group and non-heparin group
- Blood contamination area in pass 2 between the heparin group and non-heparin group
- Blood contamination area in pass 3 between the heparin group and non-heparin group
- Tissue area between passes 1, 2, and 3 in the heparin group
- Tissue area between passes 1, 2, and 3 in the non-heparin group
- Tissue area in pass 1 between the heparin group and non-heparin group
- Tissue area in pass 2 between the heparin group and non-heparin group
- Tissue area in pass 3 between the heparin group and non-heparin group
- Cell number between passes 1, 2, and 3 in the heparin group
- Cell number between passes 1, 2, and 3 in the non-heparin group
- Cell number in pass 1 between the heparin group and non-heparin group
- Cell number in pass 2 between the heparin group and non-heparin group
- Cell number in pass 3 between the heparin group and non-heparin group

Statistical Comparisons using pathologist scoring:

The Pearson's Chi-squared test will be utilized to determine if there is a significant difference in the following:

- Tissue score between passes 1, 2, and 3 in the heparin group
- Tissue score between passes 1, 2, and 3 in the non-heparin group
- Tissue score in pass 1 between the heparin and non-heparin group
- Tissue score in pass 2 between the heparin and non-heparin group

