- Tissue score in pass 3 between the heparin and non-heparin group

In a previous study the standard deviation for tissue area with fine needle biopsy of pancreatic masses was 5 mm².⁹ Based on our preliminary results and on results of

recent crossover RCT, we will assume a difference between randomized groups of 3 mm².⁵ Therefore, if the true mean difference in total tissue area between the heparin and non-heparin groups is 3 mm², we will need to study 44 subjects in the heparin group and 44 subjects in the non-heparin group, to reject the null hypothesis with 80% power and with a type I error of 0.05. To account for 10% dropouts, we will need to recruit 98 subjects.

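### The incremental diagnostic yield objective has no analysis, and the only per-pass diagnostic reading is an undefined yes/no item that is never compared with the final diagnosis

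*Combined protocol and SAP*

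**What the plan says.** Section 2 lists as a secondary objective: "Determine the incremental diagnostic yield with a second or third FNB pass as compared to a single FNB pass". Section 1 gives the reason for taking more than one pass: "multiple passes are often performed to improve diagnostic accuracy and reduce false negative results".

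Under Tissue Analysis in Section 6, a blinded pathologist answers two questions on each slide from passes 1, 2 and 3. The first is "Is a tissue diagnosis able to be made"; the second concerns tissue quality, on a scoring system still to be created. Section 8 repeats both questions and defines neither answer further.

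Section 7 lists "Final Diagnosis" among the items taken from the chart at the end of the study. No use is stated for it.

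The Section 8 outcomes cover cellularity, blood contamination, cellular yield and repeat procedures, plus exploratory correlations. The t tests cover blood area, tissue area and cell number. For pathologist readings the text says "The Pearson's Chi-squared test will be utilized to determine if there is a significant difference in the following", followed by five comparisons. All five use the tissue score: two across passes within an arm, three between arms at a given pass.

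**The concern.** The objective is stated and then disappears. No outcome, estimate or test in Section 8 corresponds to it. Incremental yield is a within-patient, cumulative quantity: what is known after pass 1, after passes 1 and 2, and after all three. None of the listed comparisons is built that way.

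The natural fallback is the yes/no item, and it does not fit the rationale. A false negative can be recognised only against a reference diagnosis. Suppose pass 1 reads as benign and pass 2 shows carcinoma. If a benign reading scores yes, pass 2 appears to add nothing. If only malignancy scores yes, a correctly identified benign lesion never registers, although eligibility in Section 4 requires only a possible solid lesion. Under either convention, right and wrong diagnoses are not distinguished.

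Section 1 promises guidance on how many passes are needed and how to divide them among uses. An incremental-yield result will be read as part of that guidance.

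**Working it through.** **The plan's own figure.** The only sizing calculation is in Section 8 and concerns tissue area: "the standard deviation for tissue area with fine needle biopsy of pancreatic masses was 5 mm²" and "if the true mean difference in total tissue area between the heparin and non-heparin groups is 3 mm²". With two-sided α = 0.05 and 80% power, n per arm = 2 × (1.960 + 0.842)² × 5² / 3² = 43.6, so 44. Then 88 / 0.90 = 97.8, so 98. Both figures reproduce, but they say nothing about diagnostic yield, for which the plan gives no rate or precision.

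**Which way a yes/no measure errs.** Take the convention that any diagnostic label scores yes. Split pass 1 into correct (C), labelled but wrong (W) and non-diagnostic (N), with C + W + N = 1. Count cumulative success once any pass is correct.

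- Yes/no gain = P(N at pass 1, any label later).
- Correct-diagnosis gain = P(not correct at pass 1, correct later).
- Gap (second minus first) = P(W at pass 1, correct later) − P(N at pass 1, only wrong labels later).

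The two terms have opposite signs, so the direction is not fixed. All rates below are assumptions.

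**Independent passes with equal rates, C = 0.85.** Yes/no gain = N(1 − N²). Correct gain = (1 − C)(1 − (1 − C)²) = 0.15 × (1 − 0.0225) = 14.7 points.

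| W | N | Yes/no gain (points) | Correct gain (points) | Gap (points) |
|---|---|---|---|---|
| 0 | 0.15 | 14.7 | 14.7 | 0 |
| 0.05 | 0.10 | 0.10 × 0.99 = 9.9 | 14.7 | 4.8 |
| 0.10 | 0.05 | 0.05 × 0.9975 = 5.0 | 14.7 | 9.7 |

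Gaps of 4.8 and 9.7 points are about 5 and 9 of the 98 recruited, or about 4 and 9 of the 88 planned after dropout.

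**Correlated passes, W = 0.05 and N = 0.10.** Let f be the share of W later corrected, q the share of N that becomes correct, and r the share of N that receives only wrong labels. Yes/no gain = N(q + r); correct gain = Nq + Wf.

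| f | q | r | Yes/no gain (points) | Correct gain (points) | Gap (points) |
|---|---|---|---|---|---|
| 0.8 | 0.8 | 0.05 | 8.5 | 8.0 + 4.0 = 12.0 | +3.5 |
| 0.5 | 0.6 | 0.1 | 7.0 | 6.0 + 2.5 = 8.5 | +1.5 |
| 0.2 | 0.6 | 0.2 | 8.0 | 6.0 + 1.0 = 7.0 | −1.0 |
| 0 | 0.6 | 0.1 | 7.0 | 6.0 + 0 = 6.0 | −1.0 |

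Passes from one lesion are unlikely to be independent, so the first table is the more extreme case. If later passes often correct wrong first readings, the yes/no measure understates the gain. If errors repeat, it can slightly overstate it. With no wrong labels there is no bias.

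**The case against.** Several points on the other side stand.

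- **The plan never says that yield will be computed from the yes/no item.** That is an inference from its being the only diagnostic reading per pass. The firm finding is that the objective has no definition, reference standard or analysis; the bias follows only if the item is used.
- **A reader might infer that a false-negative first pass is scored as a success.** This requires a benign reading to count as yes, which the documents do not settle. Section 4 also excludes a history of chronic pancreatitis, which may make misleading inflammatory readings less common.
- **A reader might infer that the pathologist comparisons look at only one pass at a time.** They do not: two of the five are across passes within an arm. They use the tissue score, however, and are not cumulative.
- **Section 3 does compare diagnoses.** If the blinded reader finds malignancy and "the diagnosis was not made on the passes obtained for clinical purposes, the patient will be notified". So the reader is expected to reach a specific diagnosis. But this is a notification step, not an analysis, and it does not use the final diagnosis.
- **The objective says yield, not accuracy.** This is fair, and the remedy should report both. The Section 1 rationale, however, is about accuracy and false negatives.
- **The final diagnosis may be circular.** Passes 1 to 3 are themselves sent to pathology as clinical specimens, so the charted diagnosis may rest on them. This limits any agreement measure and has to be reported.

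This is also one of five secondary objectives in a self-described pilot. The primary outcomes listed in Section 8, cellularity and blood contamination, are untouched.

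**Conclusion.** The concern holds as a gap in the plan for one secondary objective. Incremental diagnostic yield is promised in Section 2, Section 8 contains no analysis of it, and the one per-pass diagnostic item is undefined and not linked to the final diagnosis.

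A reader might infer that the gain from passes 2 and 3 is necessarily understated and the advice tilted towards fewer passes. The documents do not support this: the direction depends on how yes is scored and on whether errors repeat across passes. Nor can a size be fixed. Supposing that 5–15% of patients are misread at pass 1 and corrected later returns 5–15 points, which only restates the supposition. The scenarios above run from 9.7 points understated to 1.0 point overstated, all on assumed rates. The supportable statement is that the gain may be biased, probably downward if later passes correct wrong first readings, by an unknown amount.

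It is worth correcting before slides are read, since the remedy is cheap and the objective cannot otherwise be answered as stated.

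**What to change.** - Have the blinded pathologist record a diagnostic category for each pass: malignant, other neoplasm, benign or non-diagnostic. Keep the yes/no readability rate as a descriptive measure and define what counts as yes.
- Add a Section 8 paragraph deriving, for each patient, cumulative diagnostic yield and cumulative agreement with the final diagnosis after pass 1, passes 1–2 and passes 1–3. State beforehand how discordant passes are combined.
- Report the paired increments with 95% confidence intervals, overall and by arm.
- Take the final diagnosis from surgery, repeat sampling or clinical follow-up where available, state a minimum follow-up, and flag patients whose final diagnosis rests only on the study passes.

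**Cost.** One more field on the reading form and a short paragraph; the separate jars, the blinded reader and the final diagnosis are already planned. Late-enrolled patients need some follow-up, within the up to 5 years of data collection that Section 7 allows. A rule for assigning the reference diagnosis has to be written, and agreement will remain partly circular where no independent reference exists. Adding the field after reading could mean re-reading up to 3 × 98 = 294 pass specimens.

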7 DATA COLLECTION AND MANAGEMENT PROCEDURES

Collection of medical record data for this study will include the following:

Initial collection:

- Patient demographic data:
 - Age
 - Sex
 - BMI
 - Pack Years
 - Presence of Diabetes, Type 1 or 2
 - Alcohol use
 - History of Pancreatitis
 - History of IPMN (intraductal papillary mucinous neoplasms)
 - Prior Cancer History

Follow up collection (approximately 4 weeks post-procedure):

- Was patient reached for follow-up?
- Did patient develop post-procedural complications?
- Did patient need interventions for post-procedural complications?
- Was hospital admission required for post-procedure complication?
- Did patient require repeated EUS for sampling?
- Age Patient demographic data:

Chart review at end of study (after 98 patients collected)

- Development of new pancreatic disease other than cancer
- Overall survival (date of death)
- Cancer Stage
 - If resectable, did patient receive surgery?
 - If yes
 - What surgery (distal pancreatectomy vs Whipple?)

- Final surgical staging
- Tumor grade
- Chemotherapy treatment
 - Palliative, neoadjuvant, or adjuvant chemo
 - Regimen (FOLFIRINOX, Gemcitabine/abraxane, Gemcitabine/cisplatin)
- ECOG score
- Final Diagnosis

. Data will be pulled from patient's medical charts via both DataDirect and chart review. Regarding data management we will seek assistance with the MICHR database development service. The study team may collect data from each research participant for up to 5 years from when they were consented. This data will be stripped of patient name and stored using REDCap; only the study team members have access to this database. On the database, patient identity will not be discernable to the casual observer. As indicated in section 6, separate from this, a spreadsheet key matching the specimen ID to the patient name and medical record number will be kept in a password and network protected database. Only study team members will have access to this spreadsheet.

SCHEDULE OF EVENTS8 DATA ANALYSIS

Primary Outcomes

- Heparin priming increases cellularity captured in fine needle biopsies
- Heparin priming decrease blood contamination in fine needle biopsies

Secondary Outcomes

- Successive fine needle biopsy passes result in more blood contamination
- Successive fine needle biopsy passes have lower cellular yield
- Successive fine needle biopsy passes have more blood contamination
- Need for repeated procedure (at U of M)

Exploratory Outcomes

- Identify correlations in patient metadata (i.e. tumor grade, cancer stage) and tissue quality, cellular yield, and blood contamination

Tissue analysis:

H&E slides from the pass 1, 2, and 3 (which will be requested from pathology) will be compared in the following manner:

- A blinded clinical pathologist will examine each slide and determine
 - Is a tissue diagnosis able to be made?
 - Is the tissue adequate quality (pathologist will make a reference scoring system and rank specimens accordingly)

In parallel, using image processing software, the number of cells present on each H&E slide will be quantified, the amount of blood present on each H&E slide will be quantified by area quantification, and the tissue yield on each H&E slide will be quantified by area quantification.

Statistical Comparisons using image analysis:

The student *t* test will be utilized to assess if there is a significant difference in the following:

- Blood contamination area between passes 1, 2, and 3 in the heparin group
- Blood contamination area between passes 1, 2, and 3 in the non-heparin group
- Blood contamination area in pass 1 between the heparin group and non-heparin group
- Blood contamination area in pass 2 between the heparin group and non-heparin group
- Blood contamination area in pass 3 between the heparin group and non-heparin group
- Tissue area between passes 1, 2, and 3 in the heparin group
- Tissue area between passes 1, 2, and 3 in the non-heparin group
- Tissue area in pass 1 between the heparin group and non-heparin group
- Tissue area in pass 2 between the heparin group and non-heparin group
- Tissue area in pass 3 between the heparin group and non-heparin group
- Cell number between passes 1, 2, and 3 in the heparin group
- Cell number between passes 1, 2, and 3 in the non-heparin group
- Cell number in pass 1 between the heparin group and non-heparin group
- Cell number in pass 2 between the heparin group and non-heparin group
- Cell number in pass 3 between the heparin group and non-heparin group

Statistical Comparisons using pathologist scoring:

The Pearson's Chi-squared test will be utilized to determine if there is a significant difference in the following:

- Tissue score between passes 1, 2, and 3 in the heparin group
- Tissue score between passes 1, 2, and 3 in the non-heparin group
- Tissue score in pass 1 between the heparin and non-heparin group
- Tissue score in pass 2 between the heparin and non-heparin group
- Tissue score in pass 3 between the heparin and non-heparin group

In a previous study the standard deviation for tissue area with fine needle biopsy of pancreatic masses was 5 mm².⁹ Based on our preliminary results and on results of

recent crossover RCT, we will assume a difference between randomized groups of 3 mm².⁵ Therefore, if the true mean difference in total tissue area between the heparin and non-heparin groups is 3 mm², we will need to study 44 subjects in the heparin group and 44 subjects in the non-heparin group, to reject the null hypothesis with 80% power and with a type I error of 0.05. To account for 10% dropouts, we will need to recruit 98 subjects.

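### The two Section 8 primary outcomes are compared between arms only by six per-pass t tests, with no primary pass, success rule or adjustment, so whether the stated 0.05 holds depends on a rule the plan leaves open

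*Combined protocol and SAP*

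**What the plan says.** Under Primary Outcomes, Section 8 lists "Heparin priming increases cellularity captured in fine needle biopsies" and "Heparin priming decrease blood contamination in fine needle biopsies". Both are directional.

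The image-analysis test list in the same section applies Student's t test to each entry. For these two outcomes the between-arm entries run from "Blood contamination area in pass 1 between the heparin group and non-heparin group" through passes 2 and 3, and likewise for cell counts up to "Cell number in pass 3 between the heparin group and non-heparin group". The remaining entries on these variables compare passes within one arm. Section 10 refers back to Section 8, gives power 0.80 and alpha 0.05, and mentions pass number and heparin priming as variables, but states no model or decision rule.

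Two other places point to different primary variables:

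- Section 2 gives the primary objective as "Determine whether heparin priming of FNB needle improves tissue quality as compared to standard FNB". It places "Determine whether heparin priming of FNB needle improves cellularity" and "Determine whether heparin priming of FNB needle reduces blood contamination" among the secondary objectives.
- The sample-size paragraph of Section 8 is built on a between-arm difference in total tissue area. The test list covers tissue area by pass only, starting with "Tissue area in pass 1 between the heparin group and non-heparin group".

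**The concern.** The plan does not say which result would make the trial positive. Because it is silent, a significant benefit at any one pass, on either outcome, could be reported as a positive primary finding, and the choice could be made after the results are known. The trial is described as a pilot in Section 1. However, Section 2 calls it a superiority trial, and Section 8 sizes it to reject a null hypothesis at type I error 0.05. That 0.05 describes a single test. What is at stake is whether a claim that heparin priming helps carries the error rate the protocol states.

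**Working it through.** **The plan's own figure.** Inputs from the sample-size paragraph of Section 8: difference 3 mm², SD 5 mm², power 80%, type I error 0.05, dropout 10%.

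- Per arm: 2 × (1.960 + 0.842)² × 5² / 3² = 43.6, so 44. Recruited: 88 / 0.90 = 97.8, so 98. Both stated figures reproduce.
- Sidedness is not stated. One-sided 0.05 would give 35 per arm, so the test is taken as two-sided, which is 0.025 in the benefit direction.

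**Count of tests.** Two outcomes × three passes = six between-arm tests.

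**Independent tests.**

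- Any false benefit among six: 1 − 0.975⁶ = 14.1%. Any false difference, harm included: 1 − 0.95⁶ = 26.5%.
- Any false benefit among three (one outcome): 1 − 0.975³ = 7.3%. Any false difference: 1 − 0.95³ = 14.3%.

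**Correlated tests.** The documents give no correlations. Assumed: between-pass 0 to 0.9; between-outcome 0 to 0.7 in the benefit direction, with −0.3 to −0.7 as a further case, since more tissue could bring both more cells and more blood. The correlation across both pass and outcome is taken as the product. Results come from multivariate-normal simulation with 1,000,000 draws per setting, counting statistics above 1.960. In the last column one outcome truly improves by 3/5 = 0.6 SD at each pass, a shift of 0.6 × √(44/2) = 2.81, and the other does not change.

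| Between-pass, between-outcome | Any of six | Both required, neither affected | Both required, one improved |
|---|---|---|---|
| 0, 0 | 14.1% | 0.5% | 7.3% |
| 0.5, 0.5 | 11.0% | 1.5% | 6.3% |
| 0.9, 0.7 | 6.8% | 1.6% | 4.2% |
| 0.9, 0 | 8.2% | 0.2% | 3.7% |
| 0.9, −0.7 | 8.4% | 0.0% | 1.5% |

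Ranges over the whole grid:

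- Any of six: false benefit 6.8-14.1% (8.4-14.3% for negative between-outcome correlation). Any false difference is 13.6-26.5% for non-negative correlation.
- One endpoint at three passes: false benefit 4.2-7.3%; any false difference 8.4-14.3%.
- Both required, neither affected: 0.2-2.6% (0-0.4% negative).
- Both required, one improved: 3.7-7.4% (1.5-7.2% negative).

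Simulated t tests with 44 patients per arm agree: 13.9%, 11.0% and 6.8% for any of six in the first three rows.

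**With one three-pass average per outcome.** Holm gives any false difference 4.3-5.0% and false benefit 2.1-2.5% (up to 2.9% for negative correlation). Requiring both at 0.05 gives at most 2.5% when only one outcome improves.

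**The case against.** A reader might infer that the plan declares success on any one of six tests and so has a 14% error rate. The documents do not support that. They contain no decision rule, and 14.1% also needs independent tests. In each patient the three passes come from the same procedure on the same mass (Section 6), so independence is an upper-end case. The any-of-six range is one reading among several.

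A reader might also take Section 8 as settling that cellularity and blood contamination are primary. Section 2 lists them as secondary. If Section 2 governs, the six tests are secondary and the any-of-six figure does not describe primary error. That stands. It does not remove the problem, because tissue area and the pathologist's tissue score are also compared between arms at each pass separately.

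Requiring both outcomes may seem to settle the matter. When heparin affects neither outcome, the rate is indeed at or below about nominal, and mostly well below 2.5%. The protection fails when only one outcome improves, because the other still has three chances.

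The pilot label softens the consequence, but the superiority design and the sizing at 0.05 limit that argument. Finally, Section 2 hypothesizes that quality falls with pass number, so per-pass comparisons answer a stated question. That justifies keeping them as secondary, or naming one pass as primary. It does not justify leaving all of them as unranked primary tests.

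**Conclusion.** The point holds as a gap in the primary analysis, and it should be closed before data are seen. Following the listed tests at 0.05 does not secure the stated error rate, and Section 2, the Section 8 outcome list and the sample-size paragraph disagree on the primary endpoint.

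Against 2.5% for one test in the benefit direction, false benefit is about 7-14% if any one of six suffices, and 4.2-7.3% if one endpoint is kept but tested at three passes. If both outcomes are required, excess error arises when only one of them truly improves: 3.7-7.4%, or 1.5-7.2% for negative between-outcome correlation. Settling the endpoint alone is therefore not enough.

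The figures rest on the assumed correlations, on two-sided 0.05 per test and, for the last case, on an illustrative 0.6 SD effect. The absence of a primary pass, success rule and adjustment rests on the text alone.

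**What to change.** 1. Reconcile the primary endpoint across Section 2 (tissue quality), Section 8 (cellularity and blood contamination) and the sample-size paragraph (total tissue area).
2. Before data are seen, prespecify one between-arm test per primary outcome: the arm effect averaged or totalled over the three passes, or one named pass.
3. If one primary is kept, test it at 0.05. If two remain, use Holm when either suffices, or require both at 0.05.
4. Report the other per-pass and within-arm comparisons as secondary.
5. For a total or average, state how patients with fewer than three passes are handled, since Section 6 allows withdrawal during the procedure.

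**Cost.** Wording in Sections 2, 8 and 10, and no new data. There is a power cost with two primaries, because under Holm the smaller p-value must be below 0.025. Power by noncentral t at 44 per arm:

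- If 3/5 = 0.6 SD applies to the total itself, power is about 79% at 0.05 and about 70% at 0.025, whatever the between-pass correlation. Reading total as the sum over three passes is an inference; the protocol does not define it.
- If 0.6 SD applies at each pass, the SD of the three-pass mean is √((1 + 2ρ)/3) of the single-pass SD. Power at 0.025 is then 88%, 80% and 74% for ρ = 0.5, 0.7 and 0.9 (93%, 88% and 82% at 0.05).
- Averaging loses power if the effect is concentrated in later passes. For an assumed 0.2, 0.4 and 0.6 SD at ρ = 0.5, the average has 62% at 0.05, against 79% for pass 3 alone. If that pattern is expected, a named pass can be chosen.
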